7.8 Safety Evaluation

7.8.1 Adverse Events

The following analysis will be based on SS. The analysis of AEs for each vaccination of sIPV will be based on SS1_sIPV, SS2_sIPV, SS3_sIPV and the analysis of AEs for each vaccination of sIPV and

routine vaccines will be based on SS1_sIPV&Routine, SS2_sIPV&Routine, SS3_sIPV&Routine, respectively.

All AEs will be coded by using MedDRA 25.1 or later version, and be summarized by SOC and PT. This study focuses on the analysis of AEs occurring during the vaccination, which includes TEAEs occurring after (including) the first vaccination and within 28 days after the full vaccination. AEs which occurred before the first vaccination and 28 days after the full vaccination will be listed. AEs below are those that occurred during the vaccination if not otherwise specified.

The number of events, number of participants and percentage of participants reported the AEs will be calculated by groups (combined group C and combined group S), fisher's exact test will be used to test the differences between groups. The AEs will be summarized as following:

- ✓ All AEs;
- ✓ Vaccine-related AEs;
- ✓ Vaccine-unrelated AEs;
- ✓ AEs by severity (grade 1, grade 2, grade 3, grade 4, grade 5, \geq grade 2 and \geq grade 3);
- ✓ AEs by severity, related to vaccine;
- ✓ AEs by severity, unrelated to vaccine;
- ✓ AEs by onset time (30 minutes, 0-7 days, 8-28 days, 0-28 days, after 28 days);
- ✓ AEs by onset time, related to vaccine;
- ✓ AEs by onset time, unrelated to vaccine;
- ✓ AEs by doses;
- ✓ AEs by doses, related to vaccine;
- ✓ AEs by doses, unrelated to vaccine;
- ✓ AEs leading to early termination;
- ✓ AEs leading to early termination, related to vaccine.

Fisher's exact test will be used to compare the difference among groups.

When one participant experiences more than one AEs, he/she will be counted once to calculate the incidence, and the severest and most related events will be included when analyze the severity and relationship to the vaccine of AEs.

All AEs and AEs leading to early termination will be listed.

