3. OBJECTIVES AND ENDPOINTS

The objectives and endpoints of this clinical trial are as follows:

	Objectives	Endpoints
Primary	To evaluate the non-inferiority of immune response to polio vaccination, when administered concomitantly with routine vaccines	
 Seroconversion rates of neutralizing antibody against polioviruses of three serotypes, at 28 days after three doses of vaccination
	To evaluate the safety in terms of ARs (Vaccine-related AEs)	
 Incidence of adverse reactions within 7 days after each dose of vaccination
Secondary	To evaluate non-inferiority of immune response to diphtheria and tetanus antigens, when routine vaccines are administered concomitantly with sIPV	
 Sero-protection rate of IgG antibodies against diphtheria (DT) and tetanus (TT), at 28 days after vaccination
	To evaluate non-inferiority of immune response to acellular pertussis antigens, when routine vaccines are administered concomitantly with sIPV	
 Seropositivity rate of IgG antibodies against pertussis toxin (PT), Filamentous hemagglutinin (FHA), Pertactin (PRN), at 28 days after vaccination
	To evaluate other immunogenicity against diphtheria, tetanus, acellular pertussis antigens	
 GMC/GMFR of IgG antibodies against DT, TT, PT, FHA, PRN, at 28 days after vaccination
	To evaluate other immunogenicity of sIPV, when administered concomitantly with routine vaccines	
 Sero-protection rate of neutralizing antibody against polioviruses of three serotypes, at 28 days after three doses of vaccination GMT/GMFR of neutralizing antibodies against polioviruses of three serotypes, at 28 days after three doses of vaccination
	To evaluate the immunogenicity against hepatitis B and Hib, when routine vaccines are administered concomitantly with sIPV	
 Sero-protection rate of IgG antibodies against hepatitis B and Hib, at 28 days after vaccination GMC/GMFR of IgG antibodies against hepatitis B and Hib, at 28 days after vaccination
	To evaluate the immunogenicity against pneumococcal, when routine vaccines are administered concomitantly with sIPV	
 Sero-protection rate of IgG antibodies against pneumococcal, at 28 days after vaccination GMC/GMFR of IgG antibodies against pneumococcal, at 28 days after vaccination

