4.1 Overall Study Design

4.1.1 Overview of the Study

This is a multi-country, multi-center, open-labelled, randomized, controlled, extended phase III clinical trial. Totally 1440 healthy infants of 6 weeks old (42-47 days) for Bangladesh and of 6-8 weeks old (42-56 days) for Pakistan (Bangladesh and Pakistan, each includes 720 participants) are planned to be enrolled, and then randomized in a 1:1:1:1 ratio into four groups, i.e., co-administration group 1 (group C1), co-administration group 2 (group C2), staggered administration group 1 (group S1) and staggered administration group 2 (group S2).

Participants in group C1 and C2 will receive sIPV at 6,10,14 weeks old (at 4-week intervals), administered concomitantly with routine infant vaccine (may include Adsorbed Diphtheria-Tetanus-whole cell Pertussis-Hepatitis B and Haemophilus influenza type b conjugate vaccine (DTP-HepB-Hib), PCV or rotavirus vaccine in accordance with the local routine vaccination schedule). Participants in group S1 will receive sIPV at 6,10,14 weeks old, and receive routine infant vaccines at 8,12,16 weeks old (at 4-week intervals, respectively). Participants in group S2 will receive routine infant vaccines at 6,10,14 weeks old, and receive sIPV at 8,12,16 weeks old (at 4-week intervals, respectively). The sample size allocations, vaccination schedules and blood collections for each group

in different countries are shown in the tables (table 1 to table 3) below.

Table 1 Study Design for Each Group

Group	Sample Code	Size	Vaccination Schedule						Blood Collection Time	Antibody Tests Testing Item
			6 weeks	8 weeks	10 weeks	12 weeks	14 weeks	16 weeks		
C1	360	sIPV+			sIPV+			sIPV+	Baseline 18 Weeks	Neutralizing antibody against polioviruses of type 1,2,3
		Routine vaccines			Routine vaccines			Routine vaccines		
C2	360	sIPV+			sIPV+			sIPV+	Baseline 18 Weeks	Antibodies against Diphtheria, Tetanus, Pertussis (FHA, Pertactin, Pertussis toxoid), Hepatitis B, Hib, Pneumococcal antibodies*
		Routine vaccines			Routine vaccines			Routine vaccines		
S1	360	sIPV	Routine vaccines	sIPV	Routine vaccines	sIPV	Routine vaccines	sIPV	Baseline 18 Weeks	Neutralizing antibody against polioviruses of type 1,2,3
S2	360	Routine vaccines	sIPV	Routine vaccines	sIPV	Routine vaccines	sIPV	sIPV	Baseline 18 Weeks	Antibodies against Diphtheria, Tetanus, Pertussis (FHA, Pertactin, Pertussis toxoid), Hepatitis B, Hib, Pneumococcal antibodies*
Total	1440									

*Only for serotype 1, 5, 6B, 14, 19F.

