4.2 Randomization

Stratified blocked randomization was carried out in this study, taking the study site as a stratification factor. The independent randomization statistician used SAS 9.4 to generate a randomization code list. In order to minimize the probability of relevant participants being informed of the group, the paper randomization card with numbers will be used. For each eligible participant, after enrollment, the grouping information will be revealed, including the name of the vaccine and the site of vaccination.

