7.1.5 Table and Listings

- **Tables**

Excluding safety evaluation, all data will be summarized by group (i.e., C1, C2, S1 and S2). In safety evaluation, the data will be summarized by combined group C (including C1 and C2) and combined group S (including S1 and S2).

➤ **Listings**

Unless otherwise specified, listings generally include participant ID and group. Study Data Tabulation Model (SDTM) data is preferred to display in the listing. They will be sorted by group, participant ID, visit or other relevant time (e.g., start date of AE).

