7.7 Immunogenicity Evaluation

➤ **Immunogenicity evaluation for Nab against polioviruses**

The following analysis will be performed for Nab against polioviruses of serotype I, II, III between **group C1 and group S1 at 28 days after last vaccination of sIPV**, respectively:

The seroconversion (4-fold increase) rate in all participants, SCR in seronegative participants at pre-vaccination, 4-fold increase rate in seropositive participants at pre-vaccination and SPR in all participants will be estimated in each group. Clopper Pearson method will be used to calculate 95% CIs and Cochran-Mantel-Haenszel- χ^2 (CMH- χ^2) test stratified by study site (including Bangladesh 01, Pakistan 01 and Pakistan 02) will be used to test the differences between the two groups. The CMH method will be used to calculate the rate difference between (group C1 - group S1) and 95% CIs. Non-inferiority will be concluded if the lower limit of the 95% CI of SCR difference between group C1 and Group S1 >-10%.

Analysis of covariance model will be modeled to analyze Nab level against polioviruses at 28 days after last vaccination of sIPV. In this model, the log-transformed Nab data against polioviruses at 28 days after last vaccination of sIPV will be included as dependent variable, the log-transformed Nab data before vaccination as a covariate, and treatment group (including C1 and S1) and study site (including Bangladesh 01, Pakistan 01 and Pakistan 02) are the fixed effect. From the model, the LS-adjusted log-transformed Nab level against polioviruses at 28 days after last vaccination of sIPV in each group and the difference between (group C1 - group S1) will be calculated. The adjusted GMT at 28 days after last vaccination of sIPV in each group, GMT ratio between (group C1/group S1), and its 95% CIs will be obtained after inverse log-transformation.

Descriptive statistics, including geometric mean and 95% CIs, for GMT and GMFR in all participants, seronegative participants at pre-vaccination and seropositive participants at pre-vaccination will be presented by groups. The group t-test after log-transformation will be used to compare the differences between groups. The ratio of GMT between groups and their 95% CIs will be estimated as well.

The forest plot of the post-vaccination seroconversion (4-fold increase) rate for all participants in comparison (group C1 and group S1) will be plotted.

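### The primary safety endpoint is compared with an unstratified Fisher's exact test and no between-group difference or confidence interval, although randomisation is stratified by site

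*SAP*

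**What the plan says.** Protocol section 3 lists this as a primary endpoint: "Incidence of adverse reactions within 7 days after each dose of vaccination". SAP 7.1.5 says that for safety "the data will be summarized by combined group C (including C1 and C2) and combined group S (including S1 and S2"). SAP 7.8.1 then specifies the output: "The number of events, number of participants and percentage of participants reported the AEs will be calculated by groups", and "fisher's exact test will be used to test the differences between groups". The listed tables include related AEs by onset time (with a 0 to 7 day band) and by dose. No stratification factor, risk difference or interval appears. Protocol 9.3.5 gives frequency tables and names no between-group test.

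SAP 4.2 describes randomisation as stratified and blocked, "taking the study site as a stratification factor". In SAP 7.7 the immunogenicity rates are compared with a CMH test "stratified by study site (including Bangladesh 01, Pakistan 01 and Pakistan 02"). For polio and pertussis that section also gives a CMH rate difference with 95% CI.

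The routine vaccines differ by country (protocol annexes): DTP-HepB-Hib with PCV10 in Bangladesh; DTP-HepB-Hib with PCV13 and rotavirus vaccine in Pakistan. SAP 7.10 plans a safety subgroup analysis by country. Protocol 9.4 says no subgroup analysis will be done.

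**The concern.** The analysis does not follow the randomisation. If reaction rates differ between sites, a pooled test uses a variance that includes the between-site spread, although stratified allocation has removed that spread from the C versus S comparison. An exact test on top of that is conservative in its own right. Both push a reactogenicity comparison towards finding no difference, which is the less cautious error for safety.

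The second matter is reporting. A pair of percentages with a non-significant p-value is easily read as evidence of similarity. Only an interval shows what excess has been ruled out. The SAP gives one for the polio and pertussis rates but not for the primary safety endpoint.

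**Working it through.** **The plan's own figure.** The documents state no power, expected rate or margin for safety. The 233 per group in SAP 4.3 concerns polio seroconversion (a Farrington-Manning score calculation gives 232) and does not bear on this test.

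**Inputs from the documents.** Four groups of 360, so C1+C2 = 720 and S1+S2 = 720. "Bangladesh and Pakistan, each includes 720 participants", so each combined group has 720/2 = 360 infants per country. There are three sites.

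**Assumptions.** The Pakistan infants split equally, giving strata of 360/180/180 per combined group. Reaction rates are assumed, with the same rate at both Pakistan sites. The test is two-sided at 5%.

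**Why pooling costs power.** With equal stratum weight by country, the pooled variance term is p(1−p) at the average rate. The relevant within-stratum term is the average of the country values.

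- 30% and 40%: pooled 0.35 × 0.65 = 0.2275; within (0.21 + 0.24)/2 = 0.225; ratio 1.01.
- 20% and 50%: pooled 0.2275; within (0.16 + 0.25)/2 = 0.205; ratio 1.11.
- 10% and 60%: pooled 0.2275; within (0.09 + 0.24)/2 = 0.165; ratio 1.38.

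So the loss from not stratifying is negligible for a 10-point country gap and grows quickly with the gap.

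**Simulation.** The CMH statistic is [Σ(aᵢ − mᵢ/2)]² / ΣVᵢ, with Vᵢ = nᵢ² mᵢ(Nᵢ − mᵢ) / [Nᵢ²(Nᵢ − 1)]. Here aᵢ is the number of infants with a reaction in C at site i, mᵢ the total in both groups, nᵢ the number per group and Nᵢ = 2nᵢ. The first three rows used 10,000 replicates and the last three 6,000.

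| Bangladesh / Pakistan rate in S | True excess in C | Fisher power | CMH power | Gain (points) |
|---|---|---|---|---|
| 30% / 30% | 7 points | 78.1% | 79.8% | 1.7 |
| 20% / 30% | 7 points | 82.9% | 84.4% | 1.5 |
| 30% / 40% | 7 points | 76.5% | 78.6% | 2.1 |
| 20% / 50% | 7 points | 77.6% | 82.1% | 4.5 |
| 10% / 50% | 6 points | 66.4% | 76.0% | 9.6 |
| 10% / 60% | 6 points | 64.9% | 78.3% | 13.4 |

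Separate runs of 4,000 replicates gave gains of 5.1, 8.9 and 13.6 points for the last three rows, so the figures are good to about a point.

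With no true difference, Fisher's test rejected 4.2% of the time at 30%/40%, 3.4% at 20%/50%, 2.5% at 10%/50% (20,000 replicates) and 1.5% at 10%/60%. CMH rejected 4.6% to 5.0%.

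In the first three rows, an unstratified Pearson test has 79.8%, 84.2% and 78.1% power. Most of that small gap is therefore the exact test's conservatism; stratification itself adds at most 0.5 points (78.6 − 78.1).

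Under a common odds ratio of 1.4 (20,000 replicates) the pattern is the same: 74.5% versus 76.4% at 20% everywhere, 81.0% versus 83.7% at 20%/40%, and 65.8% versus 76.0% at 10%/50%. At an odds ratio of 1.7 with S rates averaging 20% to 30%, the gap is only 0.1 to 1.3 points because both tests have high power.

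**What an interval would show.** Take illustrative counts of 245/720 (34.0%) and 216/720 (30.0%). Fisher's p is 0.11. The difference is 4.0 points with standard error √(0.340 × 0.660/720 + 0.300 × 0.700/720) = 0.0246. The unstratified 95% CI is 4.0 ± 1.96 × 2.46, that is −0.8 to +8.8 points. A non-significant result would leave an excess of almost 9 points open.

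**The case against.** The strongest reply is that no formal safety test is at stake. SAP 7.6 states a hypothesis for polio seroconversion only, and protocol 9.3.5 is descriptive. Fisher's test keeps its type I error below 5%, and the gain from CMH is about 2 points unless country rates differ strongly. The documents give no reaction rates, and different pneumococcal and rotavirus vaccines do not establish a large gap. All of this stands, and it limits the point to an improvement.

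Several stronger readings are tempting but unsupported:

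- That different vaccines by country bias the comparison. Allocation is balanced within site, so country does not confound C versus S; it affects precision.
- That the missing interval lowers the chance of detecting an excess. It does not change the test; it is a reporting gap.
- That only a p-value is planned. Counts and percentages by group are planned, and a reader could work out a crude, unstratified interval from them.
- That the SAP is otherwise uniform. For diphtheria, tetanus, HepB, Hib and pneumococcal, SAP 7.7 also gives no rate difference or CI, and protocol 9.3.4 has Chi-square/Fisher for HepB, Hib and pneumococcal.

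The country subgroup in SAP 7.10 would show country-specific safety results. It does not supply a pooled stratified estimate, and it conflicts with protocol 9.4.

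A further objection has force. Group C has three vaccination visits and group S six (protocol 1.3 and 8.6), so cumulative incidence within 7 days of any dose covers three windows in C and six in S. A stratified difference would estimate that unequal comparison more precisely without repairing it.

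**Conclusion.** The point holds as a low-cost improvement, not as an error that invalidates the safety analysis. The planned test is valid but conservative. Under the assumed rates, Fisher's type I error is about 1.5% to 4.2%. Site-stratified CMH gains about 2 points of power when country rates are similar, 4 to 5 at 20% versus 50%, and about 10 to 13 at 10% versus 50% to 60%. These sizes rest on assumed reaction rates, 720 per combined group and an equal split between the Pakistan sites.

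The absence of a difference and interval depends on none of those assumptions and is the firmer half of the point. The unequal number of 7-day windows is a separate limitation that must accompany any cumulative C minus S result.

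**What to change.** In SAP 7.8.1, for any adverse reaction within 7 days and any solicited AE, specify the site-stratified risk difference (combined C minus combined S) with 95% CI and the CMH test, using the three sites named in SAP 7.7. Keep Fisher's exact test for rare preferred terms and SAEs.

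State beside the cumulative result that S has six vaccination visits and C three, so the number of 7-day windows differs and site stratification does not correct this. Reconcile SAP 7.10 with protocol 9.4 on the country subgroup.

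The cost is a few sentences in the SAP and a table column, with no new data. SAP 2.1 has the SAP finalised before database lock, so the change should be made before then.

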7.8.2 Serious Adverse Events

The number of events, number of participants and percentage of participants reported the SAEs will be calculated by groups. Fisher's exact test will be used to compare the difference among groups. The SAEs will be summarized as following:

- ✓ All SAEs;
- ✓ Vaccination-related SAEs;
- ✓ Vaccination-unrelated SAEs.

All SAEs will be listed.

7.9 Handling of Missing Data

- The missing values of immunogenicity analysis in FAS will be imputed by using Last Observation Carried Forward (LOCF) method.
- The missing values of safety evaluation will not be imputed in this study.

7.10 Subgroup Analysis

Subgroup analysis is planned for both immunogenicity evaluation and safety evaluation in participants of different study country (including Bangladesh and Pakistan).

7.11 Multiplicity

The study hypothesis in chapter 7.6 will be achieved only when the non-inferiority of seroconversion (4-fold increase) rates against all poliovirus type I, II, III are all concluded. Therefore, there is no need to correct for type I error. But there is a need to correct for type II error, in order to ensure the overall statistical power ($1-\beta$) is 80%, a corrected statistical power of 93.3% (1-20% / 3) for hypothesis test of each serotype is conducted.

7.12 Interim Analysis

No interim analysis is planned.

Version History

Version	Date	Author	Changes & Rationale
V1.0	2024-10-28	[name]	Initial Release
